8.6 Efficacy Analysis

8.6.1 Phase 1b (Dose Escalation) (PLX2853 + Carboplatin)

Data will be tabulated and evaluated by descriptive statistics. Statistical analyses for the primary objectives will be descriptive only, with no hypothesis testing. Summary tables will present results for each dose cohort. Descriptive statistics will be presented for continuous variables, and frequencies and percentages will be presented for categorical and ordinal variables.

Response to treatment will be evaluated using investigator-determined RECIST v1.1 criteria (Appendix 3).

8.6.2 Phase 2a (PLX2853 Monotherapy) and Phase 2a (PLX2853 + Carboplatin Combination)

8.6.2.1 Primary Efficacy Analysis

The primary objectives of the Phase 2a cohorts of the study are to determine the antitumor activity (ORR) of PLX2853 monotherapy or PLX2853 + carboplatin combination. Response to treatment will be evaluated using investigator-determined RECIST v1.1 criteria (Appendix 3), with a minimum interval for confirmation of CR and PR of 4 weeks. Each Phase 2a cohort will enroll up to 26 evaluable subjects using a Simon's 2-stage design in which initially 12 evaluable subjects are enrolled. In the monotherapy cohort, the safety lead in of 6 subjects dosed at the level selected for Phase 2a will be included in the group of 12 evaluable subjects for stage 1. If ≥33% DLTs are seen during the initial safety lead in, the Safety Committee will convene to consider a dose reduction. If a dose reduction is deemed appropriate, the subjects in the initial safety lead in will need to be replaced and a repeat 6 subject safety lead in will need to be conducted at this lower dose. If 2 or more responses are observed in 12 evaluable subjects, another 14 evaluable subjects will be enrolled for a total of 26 subjects to that cohort. If 6 or more responses are observed, the study has 80% power with alpha of 0.05 to reject the ORR of 10% in favor of the ORR of 30%. Recruitment will stop within a cohort if no more than 1 response is observed after the initial 12 evaluable subjects have been accrued. ORR will be summarized per cohort along with their 95% confidence intervals (CIs). A 2-sided 95% CI will be calculated for the true response rate based on the Clopper-Pearson method.

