The study will employ a standard 3 + 3 design in order to determine the MTD/RP2D taking into consideration safety, PK, and PDx data (if applicable).

Data will be tabulated and evaluated by descriptive statistics. Statistical analyses for the primary objectives will be descriptive only, with no hypothesis testing. Summary tables will present results for each dose cohort. Descriptive statistics will be presented for continuous variables, and frequencies and percentages will be presented for categorical and ordinal variables.

Response to treatment will be evaluated by investigator-determined response using RECIST v1.1 criteria.

Phase 2a (PLX2853 Monotherapy) and Phase 2a (PLX2853 + carboplatin combination):

The primary objectives of the Phase 2a cohorts of the study are to determine the antitumor activity (ORR) of PLX2853 monotherapy or PLX2853 + carboplatin combination. Response to treatment will be evaluated using investigator-determined RECIST v1.1 criteria, with a minimum interval for confirmation of CR and PR of 4 weeks. Each Phase 2a cohort will enroll up to 26 evaluable subjects using a Simon's 2-stage design in which initially 12 evaluable subjects are enrolled. In the monotherapy cohort, the safety lead in of 6 subjects dosed at the level selected for Phase 2a will be included in the group of 12 evaluable subjects for stage 1. If \geq 33% DLTs are seen during the initial safety lead in, the Safety Committee will convene to consider a dose reduction. If a dose reduction is deemed appropriate, the subjects in the initial safety lead in will need to be replaced and a repeat 6 subject safety lead in will need to be conducted at this lower dose. If 2 or more responses are observed in 12 evaluable subjects, another 14 evaluable subjects will be enrolled for a total of 26 subjects to that cohort. If 6 or more responses are observed, the study has 80% power with alpha of 0.05 to reject the ORR of 10% in favor of the ORR of 30%. Recruitment will stop within a cohort if no more than 1 response is observed after the initial 12 evaluable subjects have been accrued. ORR will be summarized per cohort along with their 95% confidence intervals (CIs). A 2-sided 95% CI will be calculated for the true response rate based on the Clopper Pearson method.

PLX2853 Protocol PLX124-03/Amendment 2

SYNOPSIS TABLE 1: PHASE 2A PLX2853 MONOTHERAPY SCHEDULE OF EVENTS

ASSESSMENTS ▼	PROCEDURE ▼	SCR1	C1		C2	C3+ ²					

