8.6.2.2 Secondary Efficacy Analyses

A 2-sided 95% CI will be calculated for the true response rate based on the Clopper-Pearson method for secondary analyses.

Secondary efficacy analyses include the following:

- DCR: The percentage of subjects with confirmed CR, PR, or SD per RECIST criteria
- PFS: The number of days from the first day of PLX2853 treatment (Cycle 1 Day 1) to the
 date of the first documented disease progression or date of death from any cause, whichever
 occurs first. The time-to-event secondary efficacy endpoint of PFS will be summarized for
 each cohort using the Kaplan-Meier method. Subjects lost to follow-up or event-free as of the
 data analysis cutoff date will be right-censored.
- DOR: The number of days from the date of first response (PR or CR confirmed at least 28 days later) to the date of the first documented disease progression or date of death from any cause, whichever occurs first.

• OS: The number of days from the first day of PLX2853 treatment (Cycle 1 Day 1) to the date of death from any cause. The time-to-event secondary efficacy endpoint of OS will be summarized for each cohort using the Kaplan-Meier method. Subjects lost to follow-up or event-free as of the data analysis cutoff date will be right-censored.

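### Does the planned 95% interval contradict the Phase 2a success rule when exactly 6 of 26 subjects respond?

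*Combined protocol and SAP*

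**What the plan says.** Section 8.6.2.1 sets up each Phase 2a cohort "using a Simon's 2-stage design in which initially 12 evaluable subjects are enrolled". The futility rule is that "Recruitment will stop within a cohort if no more than 1 response is observed after the initial 12 evaluable subjects have been accrued". With 2 or more responses, "another 14 evaluable subjects will be enrolled for a total of 26 subjects to that cohort". The final criterion is a count: at 6 or more responses the plan claims 80% power with "alpha of 0.05 to reject the ORR of 10% in favor of the ORR of 30" percent. Whether alpha is one- or two-sided is not stated.

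The section then turns to reporting: the ORR is to be summarised for each cohort with a 95% interval, and "A 2-sided 95% CI will be calculated for the true response rate based on the Clopper-Pearson method". The Statistical Considerations part of the synopsis repeats both elements. Section 8.6.2.2 names the same type of interval for the secondary analyses. No section uses an interval to declare success, and none says in so many words that the count takes precedence over it.

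**The concern.** A test and an interval reported for the same endpoint are often expected to tell the same story. Here they need not. A cohort that only just succeeds, with 6 responses in 26, would be reported as having rejected an ORR of 10% next to an interval whose lower limit is 9.0%.

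If a reader took the interval as the test, the effective criterion would become 7 of 26. That is stricter than the rule that fixed the sample size, and power at an ORR of 30% would fall from about 80% to about 69%. Section 3.2 allows up to two monotherapy cohorts and one combination cohort on a Simon design, so the boundary result could come up more than once. The matching interval, 2-sided at 90%, would agree with the rule, which makes the 95% level look like an oversight.

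**Working it through.** **Inputs (8.6.2.1).** Stage 1: n1 = 12, continue if 2 or more respond. Total n = 26, so 14 in stage 2. Reject if the total is 6 or more. Null ORR 10%, alternative 30%. Stated alpha 0.05 and power 80%.

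**Step 1: reproduce the stated figures.** With X1 ~ Bin(12, p) and X2 ~ Bin(14, p),

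P(reject) = Σ over x1 ≥ 2 of P(X1 = x1) × P(X2 ≥ 6 − x1).

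| x1 | term at p = 0.10 | term at p = 0.30 |
|---|---|---|
| 2 | 0.2301 × 0.0441 = 0.0102 | 0.1678 × 0.6448 = 0.1082 |
| 3 | 0.0852 × 0.1584 = 0.0135 | 0.2397 × 0.8392 = 0.2011 |
| 4 | 0.0213 × 0.4154 = 0.0089 | 0.2311 × 0.9525 = 0.2202 |
| 5 | 0.0038 × 0.7712 = 0.0029 | 0.1585 × 0.9932 = 0.1574 |
| 6 or more | 0.0005 | 0.1178 |
| Total (unrounded terms) | **0.0360** | **0.8048** |

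The plan's figures hold. Because 0.025 < 0.0360 < 0.05, the stated alpha fits a one-sided test and not a two-sided one. That is an inference from the operating characteristics and from the directional wording of the hypothesis.

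**Step 2: the intervals.** For x responses in n, the Clopper-Pearson limits at tail area a are the a quantile of Beta(x, n − x + 1) and the 1 − a quantile of Beta(x + 1, n − x). Take a = 0.025 for 95% and a = 0.05 for 90%.

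| Result | Rule | 95% interval | 90% interval |
|---|---|---|---|
| 5/26 | not rejected | 6.6% to 39.4% | 7.9% to 36.3% |
| 6/26 | rejected | 9.0% to 43.6% | 10.6% to 40.5% |
| 7/26 | rejected | 11.6% to 47.8% | 13.4% to 44.7% |

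The 95% interval and the rule disagree at 6/26 only. The lower limit rises with the count, so at 5 or fewer both leave 10% standing, and at 7 or more both exclude it. After an early stop (0/12 or 1/12) the interval contains 10%, in line with the rule.

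**Step 3: how often 6/26 occurs.** Replacing 6 by 7 in the Step 1 sum gives 0.0113 at p = 0.10 and 0.6866 at p = 0.30. By subtraction:

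- at 10%: 0.0360 − 0.0113 = 0.0247, and 0.0247/0.0360 = 69% of the false rejections;
- at 30%: 0.8048 − 0.6866 = 0.1182, and 0.1182/0.8048 = 14.7% of the successes, about 1 in 7.

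**Step 4: is it an artefact of ignoring the two stages?** No. Solving the Step 1 sum for the p that gives a tail of 0.025 yields a lower limit of 9.2% at 6/26; a tail of 0.05 yields 10.8%. The disagreement comes from the confidence level, not from the sampling plan.

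**Step 5: what turns on it.** Continuing after stage 1 depends on the count in 12. Rejecting 10% depends on the count in 26. The interval enters neither.

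**The case for a change.** The strongest case for a change is that 6/26 is the minimum success and not a remote possibility: if the drug works as hoped, about 1 success in 7 would be of this kind. The plan states neither the sidedness of alpha nor the precedence of the count, and it places the interval under the primary analysis. A sentence written before the data would forestall an argument over whether such a cohort succeeded, and a 90% interval would agree with the rule at every possible outcome. The cost would be two sentences and one more confidence level in the code.

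The arithmetic behind this stands, and so does the observation that sidedness is left to inference. What does not follow is that the plan is deficient. Rejecting 10% in favour of 30%, with success only at high counts, is directional on its face. The loss of power to 69% occurs only if someone substitutes a criterion that the protocol never gives. Nor does the 90% interval remove the awkward report: as long as the customary 95% interval is kept, a 6/26 cohort would still show an interval containing 10%, now beside a second one that excludes it.

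**Conclusion.** The concern does not call for a change. At 6/26 a one-sided 0.05 test rejects 10% and a 2-sided 95% interval contains it. Each is correct at its own level, and nothing obliges a descriptive interval to be the inverse of the test. Followed as written, the plan gives a sound decision (error 0.036, power 0.805) and a conventional interval estimate.

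What is missing is detail that an analyst supplies without difficulty: alpha is one-sided, the response count decides, and the 95% interval describes precision. A 90% interval would be a presentational preference with no effect on any decision.

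The size is one outcome, with a lower limit of 9.0% against the 10% null. This rests on two readings: that alpha is one-sided, inferred as above, and that the count is the only success criterion, which is the only one the documents contain. If some other document made the 95% interval the basis for success, the conclusion would have to be reconsidered; nothing in the protocol suggests that.

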8.6.2.2 Secondary Efficacy Analyses

A 2-sided 95% CI will be calculated for the true response rate based on the Clopper-Pearson method for secondary analyses.

Secondary efficacy analyses include the following:

- DCR: The percentage of subjects with confirmed CR, PR, or SD per RECIST criteria
- PFS: The number of days from the first day of PLX2853 treatment (Cycle 1 Day 1) to the
 date of the first documented disease progression or date of death from any cause, whichever
 occurs first. The time-to-event secondary efficacy endpoint of PFS will be summarized for
 each cohort using the Kaplan-Meier method. Subjects lost to follow-up or event-free as of the
 data analysis cutoff date will be right-censored.
- DOR: The number of days from the date of first response (PR or CR confirmed at least 28 days later) to the date of the first documented disease progression or date of death from any cause, whichever occurs first.

• OS: The number of days from the first day of PLX2853 treatment (Cycle 1 Day 1) to the date of death from any cause. The time-to-event secondary efficacy endpoint of OS will be summarized for each cohort using the Kaplan-Meier method. Subjects lost to follow-up or event-free as of the data analysis cutoff date will be right-censored.

8.7 Pharmacokinetics, Pharmacodynamics, Biomarkers

8.7.1 Pharmacokinetic Analysis

The PK parameters of PLX2853 will be assessed by measuring AUC from time zero to time of last observed concentration hours postdose (AUC₀-last), AUC₀-24, AUC₀-∞, C_{max}, T_{max}, T_{1/2}, and accumulation ratio at steady state.

Dose proportionality following study dosing will be explored by analyzing natural log-transformed PK variables, AUC_{0-24} , $AUC_{0-\infty}$, and C_{max} , with a linear model including the natural log-transformed dose as a covariate.

8.7.2 Pharmacodynamic and Other Biomarker Analysis

Planned biomarker analyses for PDx include, but are not limited to:

- Gene expression, nucleic acid sequencing, histochemical and/or protein analyses of plasma, peripheral blood cells, and/or tumor tissue
- Analysis of HRD status

Exploratory analysis of biomarker samples may also be performed to learn about the drug and disease properties.

No formal statistical analysis of PDx endpoints will be performed. PDx data from each assay will be listed, and the possible relationships between clinical response and PDx variables will be explored. Any biological activity will be described.

8.8 Safety Analysis

Safety variables to be assessed will include assessment of AEs, physical examinations (including weight), laboratory test results (hematology, clinical chemistry, coagulation, serum inflammation marker, and urinalysis), ECG, and vital sign measurements.

AE terms recorded on the eCRFs will be mapped to preferred terms using the Medical Dictionary for Drug Regulatory Activities (MedDRA®) version 23 or later. All TEAEs will be summarized according to the system organ class and preferred term within the organ class. TEAEs will be tallied for overall frequency (number and percentage of subjects), worst reported severity, and relationship to study drug for each preferred term per subject. SAEs will be similarly summarized. Listings of deaths, SAEs, and AEs leading to early termination of study treatment or premature withdrawal from study will also be provided.

Laboratory variables will be examined using mean change in value from baseline to scheduled time points. Laboratory values will also be categorized according to their CTCAE v5.0 toxicity grade and tabulated by worst on-study toxicity grade. The baseline value of a variable is defined as the last value obtained on or before the date and time of the first PLX2853 dose.

ECG, weight, and vital signs will also be summarized by changes from baseline to scheduled time points using descriptive statistics. Changes in QTcF will also be evaluated for the proportion of subjects with absolute values >500 msec and change from baseline >60 msec.

8.9 Interim Analysis

No formal interim analysis is planned.

9.0 ASSESSMENT OF SAFETY AND ADVERSE EVENTS

Safety and tolerability will be monitored and determined by serial physical examinations (including weight), vital signs, hematology and chemistry laboratory studies (including coagulation, serum inflammation marker, and urinalysis), ECGs, and reported AEs (including deaths and other SAEs and TEAEs). The Investigator will monitor the laboratory test findings. If any laboratory test is abnormal during the course of the study, it will be followed at the discretion of the Investigator. Abnormalities of laboratory tests are evaluated by the Investigator and assessed as either clinically significant or not clinically significant. Abnormal laboratory values deemed by the Investigator to be clinically significant and, thus, constitute or are associated with an AE, must be reported on the AE form. Abnormal laboratory values that require intervention must be reported on the AE form whether or not deemed clinically significant.

9.1 Definitions

9.1.1 Adverse Event Definition

An AE is any untoward medical occurrence in a subject administered a pharmaceutical product, which does not necessarily have a causal relationship with the treatment. An AE can be any unfavorable and unintended sign (e.g., including an abnormal laboratory finding), symptom, or disease temporally associated with the use of the study drug, whether or not it is considered to be study drug related. This includes any newly occurring event or previous condition that has increased in severity or frequency since the administration of study drug. An AE includes, but is not limited to, the following:

- Any clinically significant worsening of a preexisting condition except for events clearly consistent with progression of disease under study as described in Section 9.3.2
- An AE occurring from overdose (i.e., a dose higher than that indicated in the protocol) of a study drug, whether accidental or intentional
- An AE occurring from abuse (e.g., use for nonclinical reasons) of a study drug
- An AE that has been associated with the discontinuation of the use of a study drug

Any treatment-emergent abnormal laboratory result which is clinically significant, i.e., meeting 1 or more of the following conditions, should be recorded as a single diagnosis on the AE page in the eCRF:

- Accompanied by clinical symptoms
- Leading to a change in study medication (e.g., dose modification, interruption, or permanent discontinuation)
- Requiring a change in concomitant therapy (e.g., addition of, interruption of, discontinuation of, or any other change in a concomitant medication, therapy, or treatment)

AEs will be graded in severity according to CTCAE v5.0 criteria.

9.1.2 Serious Adverse Event Definition

An SAE is any AE occurring at any dose and regardless of causality that:

- Results in death
- Is life-threatening. Life-threatening means that the subject was at immediate risk of death from the reaction as it occurred, i.e., it does not include a reaction which hypothetically might have caused death had it occurred in a more severe form.
- Requires in-subject hospitalization longer than 24 hours or prolongation of existing hospitalization (see clarification in the paragraph below on planned hospitalizations). An emergency room visit without hospitalization is not considered a hospitalization.
- Results in persistent or significant disability/incapacity. Disability is defined as a substantial disruption of a person's ability to conduct normal life functions.
- Is a congenital anomaly/birth defect
- Is an important medical event. An important medical event is an event that may not result in death, be life-threatening, or require hospitalization but may be considered an SAE when, based upon appropriate medical judgment, it may jeopardize the subject and may require medical or surgical intervention to prevent 1 of the outcomes listed in the definitions for SAEs. Examples of such medical events include allergic bronchospasm requiring intensive treatment in an emergency room or at home, blood dyscrasias or convulsions that do not result in in-subject hospitalization, or the development of drug dependency or drug abuse.

Clarification should be made between the terms "serious" and "severe" because they ARE NOT synonymous. The term "severe" is often used to describe the intensity (severity) of a specific event (as in mild, moderate, or severe myocardial infarction); the event itself, however, may be of relatively minor medical significance (such as a severe headache). This is NOT the same as "serious," which is based on subject/event outcome or action criteria described above and are usually associated with events that pose a threat to a subject's life or functioning. A severe AE does not necessarily need to be considered serious. For example, persistent nausea of several hours' duration may be considered severe nausea but not an SAE. On the other hand, a stroke resulting in only a minor degree of disability may be considered mild but would be defined as an SAE based on the above noted criteria. Seriousness (not severity) serves as a guide for defining regulatory reporting obligations.

9.2 Procedures for Recording and Reporting Adverse Events and Serious Adverse Events

All AEs spontaneously reported by the subject and/or in response to an open question from study personnel or revealed by observation, physical examination, or other diagnostic procedures will be recorded on the appropriate page of the CRF. Any clinically relevant deterioration in

laboratory assessments or other clinical finding is considered an AE and must be recorded on the appropriate pages of the CRF. When possible, signs and symptoms indicating a common underlying pathology should be noted as 1 comprehensive event.

All SAEs, as defined in Section 9.1.2, that occur during the course of the study as defined in Section 9.3 must be reported within 1 working day of awareness by using the SAE Report Form. All SAEs and deaths must be reported whether or not considered causally related to the study drug, except for events clearly consistent with progression of disease under study as described in Section 9.3.2. SAEs and deaths will be reported by completing the SAE Report Form and by emailing (fax as back-up) the completed SAE Report Form to the designated recipient (Section 7.1.1). A sample of the SAE Report Form may be found in the Study Reference Manual. Follow-up information on the SAE may be requested by Plexxikon. SAEs reported to Product Safety must match the data provided on the eCRF. Contact information will be listed on the SAE Report Form.

Planned hospital admissions or surgical procedures for an illness or disease which existed before the subject was enrolled in the study or before study drug was given are not to be considered AEs unless the condition deteriorated in an unexpected manner during the study (e.g., surgery was performed earlier or later than planned).

For both serious and non-serious AEs, the Investigator must determine both the intensity of the event and the relationship of the event to study drug administration.

Intensity for each AE, including any laboratory abnormality, will be determined by using the NCI CTCAE v5.0, as a guideline, wherever possible. The criteria are provided in the Study Reference Manual. In those cases where the NCI CTCAE criteria do not apply, intensity should be defined according to the following criteria:

Mild Awareness of sign or symptom, but easily tolerated

Moderate Discomfort enough to cause interference with normal daily activities

Severe Inability to perform normal daily activities

Relatedness to study drug administration will be determined by the Investigator responding to the question, 'Is there a reasonable possibility that the AE is associated with the study drug?' Relatedness to study drug administration will be graded as "probably," "possibly," or "not related," as follows:

Not Another cause of the event is most plausible;

Related OR

Clinically plausible temporal sequence is inconsistent with the onset of the

event and the study treatment administration;

OR,

A causal relationship is considered biologically implausible.

Possibly Related An event that follows a reasonable temporal sequence from administration of the study treatment or a known or expected response pattern to the suspected drug, but that could readily have been produced by a number of

other factors.

Probably Related An event that follows a reasonable temporal sequence from administration of the study treatment,

AND,

There is a biologically plausible mechanism for study treatment causing or contributing to the AE,

AND,

The event could not be reasonably explained by the known characteristics of the subject's clinical state.

In addition, the relationship may be confirmed by improvement on stopping the study treatment and reappearance of the event on repeated exposure.

